8.8 Final Visit (all subjects)

At the Final Visit (FV) assessments are as follows:

- Vital signs
- Body weight
- Physical examination
- Neurological examination
- 12-lead ECG (mandatory, except if the FV follows an EDV where ECG results were normal)
- IVRS/IWRS
- Subject's DRC retrieval
- Seizure counts (collected on the subject's DRC on a daily basis)
- Laboratory safety assessments (mandatory, except if the FV follows an EDV where laboratory results were normal): hematology, blood chemistry, urinalysis, and urine pregnancy test (if applicable)
- AE reporting
- C-SSRS
- Medical procedures
- Concomitant AEDs
- VNS settings
- Concomitant non-AEDs
- Study drug return/accountability
- End of study status

The FV is not applicable to subjects who convert to commercial BRV (if, when, and where available).

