10.1.2.3 Additional procedures for reporting SAEs

If an SAE is reported, UCB must be informed within 24 hours of receipt of this information by the site (see contact information for SAE reporting listed in the **SERIOUS ADVERSE EVENT REPORTING** section at the front of the protocol). The Investigator must forward to UCB (or its representative) a duly completed “Investigator SAE Report Form for Development Drug” (SAE report form) provided by UCB, even if the data are incomplete, or if it is obvious that more data will be needed in order to draw any conclusions. Information recorded on this form will be entered into the global safety database.

It is important for the Investigator, when completing the SAE report form, to include the assessment as to a causal relationship between the SAE and the IMP administration. This insight from the Investigator is very important for UCB to consider in assessing the safety of the IMP and in determining whether the SAE requires reporting to the regulatory authorities in an expedited manner.

Additional information (eg, autopsy or laboratory reports) received by the Investigator must be provided within 24 hours. All documents in the local language must be accompanied by a translation in English, or the relevant information included in the same document must be summarized in the Investigator SAE report form.

The Investigator is specifically requested to collect and report to UCB (or its representative) any SAEs (even if the Investigator is certain that they are in no way associated with the IMP), up to 30 days from the end of the study for each subject, and to also inform participating subjects of the need to inform the Investigator of any SAE within this period. Serious AEs that the Investigator thinks may be associated with the IMP must be reported to UCB regardless of the time between the event and the end of the study.

Upon receipt of the SAE report form, UCB will perform an assessment of expectedness of the reported SAE. The assessment of the expectedness of the SAE is based on the IB.

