- Down-Titration Period (up to 4 weeks):

---

- If the subject is discontinuing study drug, the Investigator will first plan an EDV followed by the progressive down-titration of study drug.
- During the Down-Titration Period, the BRV dose may be decreased in steps of a maximum of 50mg/day on a weekly basis. A last down-titration step at 25mg/day for 1 week should be included prior to the 2-week Study Drug-Free Period.
- 2-week Study Drug-Free Period: After completion of the Down-Titration Period, or for those subjects who for extenuating circumstances do not complete a Down-Titration Period, the subject will be required to enter a 2-week Study Drug-Free Period, followed by a Final Visit (FV).

Subjects who will be converted to the commercial BRV product will complete an End of Study Visit without entering the Down-Titration Period or the 2-week Study Drug-Free Period and will not complete an FV.

Visits should occur on the specified Visit/Week. A  $\pm 7$  day window for each specified Visit/Week is allowed, provided the subject has adequate investigational medicinal product (IMP) to sustain the visit window. The end of the study is defined as the date of the last visit of the last subject in the study.

EP0085 will continue until the market approval of BRV, or until the sponsor decides to close the study, whichever comes first. In the event that market approval is not requested or obtained in the participant country, the subject will be able to continue in EP0085 for two years after entering EP0085.

In Japan, EP0085 will continue as a postmarketing clinical study (Phase 4) after the date of approval of BRV for the partial seizure indication.

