After completion of the Down-Titration Period, or for those subjects who for extenuating circumstances do not complete a Down-Titration Period, the subject will enter a 2-week Study Drug-Free Period, followed by a Final Visit.

A subject is considered entering the Study Drug-Free Period if the subject has at least 1 contact (scheduled visit, unscheduled visit, or telephone contact) after the date of last dose of BRV. The 2-week Study Drug-Free Period starts 1 day after the date of last dose of BRV and ends on the date of Final Visit, irrespective of entering the Down-Titration Period.

A subject is considered as completed if this subject completes all scheduled visits as defined in the protocol or converts to commercial BRV without a Down-Titration Period (where commercial BRV is available).

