## **9.2 Primary safety variables**

### **9.2.1 Definition of treatment-emergent adverse events**

AEs will be classified as either pre-treatment or treatment-emergent. Pre-treatment AEs are defined as AEs which had onset prior to the date of the first dose of BRV in EP0085 study. Treatment-emergent AEs (TEAEs) are defined as AEs that had onset on or after the day of first BRV dose in EP0085 study. AEs with an incomplete onset date will be classified as TEAEs if the month and year of onset (when only the month and year are specified) is the same as the month and year of the first BRV dose or the year of onset (when only year is specified) is the same as the year of first BRV dose.

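### The Study Drug-Free Period rule in SAP 3.2.5 does not carry the SAP 2.3 exclusion of subjects who convert to commercial BRV, and gives no end date when there is no Final Visit

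*SAP*

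**What the plan says.** Two parts of the SAP deal with what happens after the last study dose.

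- **SAP 2.3 (Study design and conduct)** states that converters to commercial BRV have an End of Study Visit "without entering the Down-Titration Period or the 2-week Study Drug-Free Period and will not complete an FV". Protocol 8.8 agrees about the visit: "The FV is not applicable to subjects who convert to commercial BRV (if, when, and where available".
- **SAP 3.2.5 (Study periods)** gives the rule that assigns data to periods. It opens by describing who is meant to enter the Study Drug-Free Period: "After completion of the Down-Titration Period, or for those subjects who for extenuating circumstances do not complete a Down-Titration Period". The entry rule that follows is wider: "A subject is considered entering the Study Drug-Free Period if the subject has at least 1 contact (scheduled visit, unscheduled visit, or telephone contact", where the contact must come after the date of the last BRV dose. The period starts the next day and "ends on the date of Final Visit, irrespective of entering the Down-Titration Period".

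Converters are mentioned in 3.2.5 only as one kind of completed subject. They are not an exception to the entry rule.

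**The concern.** The exclusion sits in the protocol summary, and the rule a programmer would code does not contain it. SAP 13.4 (Amendment 4) records that the converter paragraph was added to 2.3, and none of the changes listed there touches 3.2.5. It looks like an update made in one place only.

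The by-period tables are at stake. SAP 9.2.2 produces the TEAE overview and the tables of incidence, maximum intensity, relationship, serious events, events of special interest, dose change and COVID-19 vaccination both overall and by study period, assigned by onset date. SAP 5.1 reports disposition by period. A subject who moved straight to the marketed product should not be shown in these outputs as off drug. Two programmers, one following 2.3 and one following 3.2.5, could produce different safety tables from the same data.

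**Working it through.** The plan gives no figure to reproduce, so the check applies the date rules to a converter. Let D be the date of the last study dose.

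**Inputs**

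- Last dose means the last dose taken in the EP0085 study periods (SAP 3.2.1), so later commercial BRV does not move D.
- Entering Down-Titration requires an Early Discontinuation Visit and at least one study dose after it (SAP 3.2.5). A converter has neither.
- Without Down-Titration, the Evaluation Period ends on D (SAP 3.2.5).
- A converter has no Final Visit (SAP 2.3, Protocol 8.8).
- TEAEs "are defined as AEs that had onset on or after the day of first BRV dose in EP0085 study" (SAP 9.2.1). No upper time limit is given.

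**Case A: End of Study Visit on or before D, and no later contact.** The entry rule is not met. The converter stays out of the Study Drug-Free Period, and 3.2.5 agrees with 2.3.

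**Case B: any contact on D+1 or later.** This could be an End of Study Visit the day after the last study tablet, or an adverse event follow-up call. Protocol 10.1.3 says follow-up usually continues for 30 days after the study drug stops.

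1. The entry rule is met.
2. The period starts on D+1, when the subject may already be on commercial BRV.
3. The end date is the date of a visit that does not take place, so it is undefined.
4. A TEAE starting after D is placed under Study Drug-Free by its onset date.
5. Disposition by period shows the subject as having started this period with nothing to mark completion, although 3.2.5 counts the same subject as having completed the study.

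The missing end date has a practical effect. Serious events are collected "up to 30 days from the end of the study for each subject" (Protocol 10.1.2.3). If a converter's study ends on D, collection runs to D+30. A 2-week period would have closed at D+14, so events from a further 30 − 14 = 16 days have no boundary to keep them out.

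**Case C: a non-converter with a contact after D but no Final Visit.** The period again starts on D+1 and has no end date, so this gap is not confined to converters.

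**Reach**

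- *Affected:* Study Drug-Free numerators in the by-period TEAE tables, and by-period disposition.
- *Unclear:* the overall TEAE tables. SAP 9.2.2 builds these by combining the Evaluation, Down-Titration and Study Drug-Free Periods. If converters are kept out of the last of these, the SAP does not say whether an event after D still counts overall.
- *Not affected:* TEAE percentages are taken over the Safety Set (SAP 9.2.2.1), so denominators do not move. The 3-month TEAE summaries stop at the last dose (SAP 9.2.2). Efficacy uses Evaluation Period records (SAP 8).

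**Number of subjects.** The documents give neither the number of converters nor the share with a contact after D. The possible range is 0% to 100% of converters.

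**The case against.** The strongest reply is that SAP 2.3 settles the matter. It says in terms that converters do not enter this period, and the opening sentence of the 3.2.5 definition also points to subjects coming off drug. A reader might infer from 3.2.5 alone that the SAP plans to analyse everyone who switched as drug-free. The documents do not support that: the stated intent is exclusion, and the literal rule catches only converters with a contact after the last study dose. The narrower point stands, because the sentence that assigns data contains no exclusion.

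It can also be said that the trigger may be uncommon. Dosing is morning and evening, and Protocol 10.2 says study medication must not be delayed for fasting, so a compliant subject may take a dose on the visit day. The visit then falls on D and does not count. Protocol 10.1.2.3 asks for serious events to be reported but schedules no call, and new events recorded after a converter's End of Study Visit would be mainly serious ones. All of this limits the size. It does not remove a visit on D+1 or a follow-up call about an ongoing event.

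Two further inferences fail. A reader might think that misclassified converters dilute the Study Drug-Free percentages, but the denominator is the Safety Set. A reader might also think this table is the only view of events after BRV stops. All TEAEs are listed (SAP 9.2.2.1), and the relative-day convention marks post-treatment days with a plus sign (SAP 3.2.2).

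**Conclusion.** The point holds as an inconsistency between SAP 2.3 and SAP 3.2.5. It should be corrected because the rule as written gives a classification that the SAP itself says is wrong. Its effect is confined to by-period TEAE numerators and by-period disposition, with an open question about the overall TEAE table. The number of subjects cannot be estimated from the documents. Planned enrolment (127 of 217 in Japan) is not a count of converters and should not be used as one.

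This rests on three assumptions: that the tables are programmed from 3.2.5 as written, that contacts after the last study dose are present in the analysis data, and that converters start commercial BRV without a gap. The documents confirm none of these. If the first or second fails, no converter is misclassified in practice, but the contradiction in the text and the missing end date remain.

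**What to change.** In SAP 3.2.5:

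1. Add to the entry rule: *except subjects who convert to commercial BRV, who do not enter the Study Drug-Free Period regardless of later contacts.*
2. List converters' adverse events with onset after the last study dose separately, and state whether they count in the overall TEAE table.
3. Define a fallback end date, for example the date of last contact, for any other entrant without a Final Visit.

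The cost is a few sentences and one derivation. The derivation needs conversion to be identifiable in the CRF data. SAP 3.2.5 mentions only complete and dropout categories on the Study Termination form, so the sponsor should confirm where conversion is recorded. Slightly fewer subjects may be shown in the Study Drug-Free Period. No new data collection is needed if conversion status is already captured.

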### 3.2.6 Monthly time intervals

In terms of the analysis, a month is defined as 30 days and time intervals based on monthly durations are defined as a multiple of 30 days (eg, 12 months is defined as 360 days). The following definitions of 3-month intervals are based on 30-day months where the date of first dose of BRV is Day 1:

Interval	Duration Definition
3-month interval	
Month 1-3	Day 1-90
Month 4-6	Day 91-180
Month 7-9	Day 181-270
Month 10-12	Day 271-360

Subsequent 3-month intervals are defined in a similar manner. Three-month intervals will be used for analyses of efficacy (except for continuously seizure-free) and TEAE summaries.

For the analysis of efficacy outcomes, a subject is included in the analysis of a 3-month interval if the last dose of study drug during the Evaluation Period of EP0085 is equal or

greater than the last day of the 3-month time interval and the seizure diary was completed for at least 1 day during the 3-month interval over the Evaluation Period.

For TEAE summaries, a subject is included in the analysis of a 3-month interval if the last dose of study drug in whole period of EP0085 is equal or greater than the first day of the 3-month time interval (as N for the time interval) and with at least one specified TEAE within the 3-month interval (as n in the summary tables according to the AE onset date).

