6.3 Withdrawal criteria

Subjects are free to withdraw from the study at any time, without prejudice to their continued care.

Subjects should be withdrawn from the study if any of the following events occur:

- Withdrawal for safety reasons by the Investigator such as a worsening of the seizure profile, eg, occurrence of status epilepticus, seizure clustering or generalized tonic-clonic seizure, if unknown for the subject

- Subject develops an illness that would interfere with his/her continued participation.
- Subject is noncompliant with the study procedures or medications in the opinion of the Investigator.
- Subject takes prohibited concomitant medications as defined in this protocol.
- Subject or legal guardian withdraws his/her consent.
- There is confirmation of a pregnancy during the study, as evidenced by a positive pregnancy test.
- The sponsor or a regulatory agency requests withdrawal of the subject.
- In the event of a suicide attempt, the subject should be referred immediately to a Mental Healthcare Professional and must be withdrawn from the study.

Subject has active suicidal ideation without specific plan as indicated by a positive response (“Yes”) to Question 4 of the “Since Last Visit” version of the C-SSRS. The subject should be referred immediately to a Mental Healthcare Professional and may be withdrawn from the study based upon the Investigator’s judgment of benefit/risk of continuing the subject in the study/on study medication.

Subject has active suicidal ideation with a specific plan as indicated by a positive response (“Yes”) to Question 5 of the “Since Last Visit” version of the C-SSRS. The subject should be referred immediately to a Mental Healthcare Professional and must be withdrawn from the study.

Investigators should attempt to obtain information on subjects, in the case of withdrawal or discontinuation. The Investigator should make effort (at least 1 phone call and 1 written message to the subject) and document his/her effort (date and summary of the phone call and copy of the written message in the source documents), to complete the final evaluation. All results of these evaluations and observations, together with a narrative description of the reason(s) for removing the subject, must be recorded in the source documents. The eCRF must document the primary reason for withdrawal or discontinuation.

Investigators should contact the Medical Monitor, whenever possible, to discuss the withdrawal of a subject in advance.

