7.8.3 Rescue medication

The rescue medication(s) which the dosage form is suppository, injection, and enema preparation are permitted during the study for sudden aggravation or cluster seizures, and if the subject's condition requires rescue medication(s) during minor surgical procedures in a relatively short time. The use of rescue medication is permitted only once a week for a maximum of 4 weeks to control seizures; if the frequency exceeds once a week, the subject will be discontinued from the study.

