#### 2.1.2 Secondary objective

The secondary objective is to evaluate the maintenance of efficacy of BRV over time.

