### 8.2.2 Analysis of percent reduction of 28DPSF

The percent reduction of 28DPSF from Baseline will be summarized by descriptive statistics as continuous parameters (refer to the Section 3.1) by study group. The analysis time intervals will be 3-month periods over the Evaluation Period. In addition, the percent reduction of 28DPSF all over the Evaluation Period will be summarized in the same way.

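### The 3-month efficacy tables omit the interval in which a subject stops brivaracetam, conflict with the responder denominator in SAP 8.2.3, and have no fixed-cohort companion

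*SAP*

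**What the plan says.** The secondary objective concerns the time course: "The secondary objective is to evaluate the maintenance of efficacy of BRV over time" (SAP 2.1.2). SAP 3.2.6 states the scope of the intervals: "Three-month intervals will be used for analyses of efficacy (except for continuously seizure-free) and TEAE summaries". For percent reduction, SAP 8.2.2 says "The analysis time intervals will be 3-month periods over the Evaluation Period"; 8.2.1 and 8.2.3 do likewise for seizure frequency and responders.

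Three rules bear on who is counted in an interval:

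- **Efficacy, SAP 3.2.6.** The last Evaluation Period dose must be equal to or "greater than the last day of the 3-month time interval and the seizure diary was completed for at least 1 day" in the interval.
- **TEAEs, same section.** It is enough that "the last dose of study drug in whole period of EP0085 is equal or greater than the first day of the 3-month" interval.
- **Responders, SAP 8.2.3.** The denominator is everyone with at least one seizure assessment in the interval, with no last-day condition.

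SAP 4.1 applies no missing-data rule and analyses efficacy on the data that are available.

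Stopping can depend on the outcome. Protocol 6.3 lists "Withdrawal for safety reasons by the Investigator such as a worsening of the seizure profile" among the reasons for withdrawal. Protocol 7.8.3 says of rescue medication that "if the frequency exceeds once a week, the subject will be discontinued from the study".

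**The concern.** The last-day condition works as an all-or-nothing filter at the point where a subject leaves. A subject who stops on Day 89 with 89 completed diary days is in no efficacy interval. A subject dosed on Day 90 with one completed diary day is in Months 1-3. That fits poorly with analysing data as available, and for responders it contradicts 8.2.3, so two programmers could produce different responder tables from the same SAP.

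What is at stake is how the maintenance objective is read. Each later interval describes those still on drug. If subjects who do poorly leave more often, a flat or rising curve can reflect who remains and not sustained effect. No planned efficacy table follows a fixed set of subjects from interval to interval, so a reader of the interval tables cannot separate the two explanations.

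**Working it through.** The plan gives no response or leaving rates. Its one design figure, planned enrolment, reproduces (90 + 7 + 30 = 127 in Japan; 127 + 90 = 217) and is not in dispute.

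**Step 1: the rule applied to a last Evaluation Period dose day.** Efficacy interval m (Days 90(m-1)+1 to 90m) needs last dose ≥ 90m. TEAE interval m needs last dose ≥ 90(m-1)+1; the table assumes no later dosing in down-titration.

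| Last dose (Day) | Efficacy intervals | TEAE intervals |
|---|---|---|
| 60 or 89 | none | 1 |
| 90 | 1 | 1 |
| 150 or 179 | 1 | 1, 2 |
| 180 | 1, 2 | 1, 2 |

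The stopping interval survives only if the last dose falls on its final day.

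**Step 2: the visit calendar.** First intake is on the evening of the Entry Visit (Protocol 7.2), so that day is Day 1 and the nominal visit day is 7 × week + 1, with a ±7-day window. Visits use 28-day months (SAP Table 1); intervals use 30-day months (SAP 3.2.6).

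| Visit | Nominal day | Window | Interval ends | Follow-up left out on the nominal day |
|---|---|---|---|---|
| V4 (W12) | 85 | 78-92 | 90 | 85 days |
| V5 (W24) | 169 | 162-176 | 180 | 169 - 90 = 79 days |
| V6 (W36) | 253 | 246-260 | 270 | 253 - 180 = 73 days |
| V7 (W48) | 337 | 330-344 | 360 | 337 - 270 = 67 days |

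A subject whose Evaluation Period ends at V5, V6 or V7 loses that whole interval anywhere in the window. At V4 this holds on the nominal day; only a V4 on Days 90-92 could keep Months 1-3.

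**Step 3: effect on the responder curve (illustration).** Assumed inputs: 45% responders at entry, nobody changes status, and per interval 3% of responders and 10% of non-responders leave. With k completed intervals of leaving:

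rate(k) = 0.45 × 0.97^k / (0.45 × 0.97^k + 0.55 × 0.90^k)

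The last-day rule uses k = m; a first-day rule uses k = m - 1. The fixed-denominator share is 0.45 × 0.97^m.

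| Interval | Last-day rule | First-day rule | On drug and responding, of all who started |
|---|---|---|---|
| Months 1-3 (m = 1) | 0.4365/0.9315 = 46.9% | 45.0% | 43.65% |
| Months 10-12 (m = 4) | 0.3984/0.7592 = 52.5% | 50.6% | 39.8% |
| Months 22-24 (m = 8) | 0.3527/0.5894 = 59.8% | 58.0% | 35.3% |

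At Months 22-24 the rise above 45% is 14.8 points under the last-day rule and 13.0 points under the first-day rule. The clause therefore contributes about 1.8 points there (1.9 in the two earlier rows). With 6% leaving among non-responders, the Months 22-24 figures are 51.3% and 50.5%, a difference of 0.8. With equal leaving rates the curve stays at 45%.

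**Step 4: sensitivity.** The same model with 217 subjects and an assumed 40% responders gives, at Months 22-24:

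| Leaving per interval, responders / non-responders | Last-day | First-day | Fixed denominator |
|---|---|---|---|
| 3% / 8% | 50.4% | 49.1% | 31.3% |
| 2% / 12% | 61.2% | 58.6% | 34.0% |
| 6% / 6% | 40.0% | 40.0% | 24.4% |
| 8% / 3% | 30.4% | 31.5% | 20.5% |

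The clause moves the rate by 1.3 to 2.6 points when non-responders leave faster, by nothing when rates are equal, and by 1.1 points the other way when responders leave faster.

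**The case against.** The strongest case against is that the last-day clause does little. On the assumed inputs, 13.0 of the 14.8 points remain after switching to a first-day rule, because they come from summarising whoever is still on treatment, which SAP 4.1 adopts openly. That stands, and it is why changing the clause alone is not enough.

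The data are also not lost to the report. Diary days before stopping enter the whole-Evaluation-Period summaries of seizure frequency and percent reduction (SAP 8.2.1, 8.2.2), and subject listings are planned (3.1). SAP 5.4 plans Kaplan-Meier time to discontinuation, including for lack of efficacy, 5.1 gives disposition by 6-month periods, and 8.2.4.1 reports continuous seizure freedom in 6-month steps. All true. But the whole-period summaries show no time course, Kaplan-Meier shows retention and not response, and the seizure-freedom percentages are themselves restricted to subjects exposed for the full interval. None of these corrects the 3-month curves.

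The comparison with the TEAE rule has limits. An event count tolerates partial intervals; a rate scaled to 28 days does not. One diary day with one seizure gives 1/1 × 28 = 28 seizures per 28 days, in tables that report means. That stands, and it calls for a minimum number of diary days.

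Finally, all summaries are descriptive and no hypothesis is tested, so no formal inference is affected.

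**Conclusion.** The point holds as a defect in the interval rule and a gap in the planned tables. The stopping interval is left out, a subject stopping before Day 90 is in no 3-month efficacy interval under 3.2.6, and 3.2.6 and 8.2.3 disagree on the responder denominator. In addition, 8.2.3 names only 3-month periods, although SAP 2.2.2 defines the responder rate over the Evaluation Period. If 3.2.6 governs, an early stopper appears in no responder table that 8.2.3 specifies.

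A reader might infer more than the documents support:

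- **That the curve will rise.** It can rise, if non-responders leave more often. The protocol makes that plausible but gives no rates; equal rates give a flat curve and reversed rates a falling one.
- **That the last-day clause causes the rise.** Under the main assumed rates it adds about 2 points; most of the drift is ordinary attrition.
- **That every failure is deleted.** A subject who worsens but stays on drug is kept, and a subject who ends administratively mid-interval is also dropped.

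The sizes rest on assumed response shares and leaving rates and on constant individual response, which is a simplification because doses and concomitant drugs may change. The calendar result rests only on the documents' day definitions. This should be changed, but it does not threaten the primary safety objective.

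**What to change.** 1. **One inclusion rule.** In SAP 3.2.6 and 8.2.3, include a subject in an efficacy interval on the basis of available Evaluation Period diary days in that interval, with a stated minimum number of days so that very short partial intervals do not give extreme 28-day rates. Show n for every interval.
2. **Whole-period responder rate.** Add it to SAP 8.2.3, as SAP 2.2.2 defines it.
3. **Fixed cohorts.** In SAP 8.2.1 to 8.2.3, repeat the interval tables for subjects with at least 12 months, and with at least 24 months, in the Evaluation Period. These cohorts are still selected for staying, but their composition does not change across the period shown.
4. **Sensitivity responder table.** Keep subjects who stopped for lack of efficacy or an adverse event in later denominators as non-responders. Remove administrative endings (conversion to commercial product, study closure) from the time they ended. State how other reasons for stopping are handled. The separation matters: in the equal-rate scenario above, counting every leaver as a non-responder takes 40.0% down to 24.4%.

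Cost: SAP wording and a few extra tables from variables already planned. Partial intervals will be somewhat noisier, and later-interval rates are likely to look less favourable.
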